### **4.3 Treatment Assignment Procedures**

#### **4.3.1 *Randomisation Procedures***

Randomisation will be at the patient level, with a 1:1 ratio between groups, using randomly varied permuted blocks, stratified by sex, hospital, treatment intent (curative/palliative) and computer literacy (defined as regular access to a computer/tablet/smart phone and use of email  $\geq 1$ /week vs. less often) as this was shown to be important in previous trials [8, 9]. When a participant completes the Baseline Study Questionnaire, the central web-based database will automatically apply the next relevant record in the allocation sequence, as we have done previously [24-26].

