## 5. **STUDY INTERVENTION**

### 5.1 **Intervention**

The full PROMISE intervention combines the e-PROM tools that participants will complete (5.1.1 and 5.1.2) and the associated implementation strategies (5.1.3). The e-PROM tools use validated instruments (DT and ESAS) that have been used in previous studies, are currently being used in the PROMPTCare system in New South Wales [27-29] and are recommended for use nationally by the Cancer Survivorship Group of the Clinical Oncology Society of Australia (COSA).

In addition to their usual care (Section 5.2), participants randomised to the intervention will be oriented to the use of the e-PROM tool (*My Health My Way* at PAH, TVH; *AboutMe* at RBWH, GCH) at their first treatment visit post-randomisation. A reminder service built into the e-PROM systems will prompt participants to complete the tool 48-72 hours before each subsequent clinic visit (for treatment or follow-up), as previous reports identify this as a feasible time frame for health services to action e-PROM data entered [30]. Participants will also be encouraged to complete the tool monthly between clinic visits to monitor their own progress and facilitate early detection of new problems or exacerbation of existing problems.

When participants arrive for their appointment, the site nurse will check the summary report, to ensure the tool has been completed and, if not, they will help the participant to complete it prior to seeing their clinician. Where feasible, they will give the participant a print-out of the report to take in when they see their clinician; the clinician will also be able to access the report electronically. The report will detail the most recent symptoms entered and their severity (severe, moderate, normal/mild according to standard cut-points) as well as trends over time. Hospital-specific protocols (co-designed with clinical staff – see Section 5.3) will also be used to generate a summary patient-risk profile (e.g. urgent, high, medium, low [30]) and provide recommendations for review/referral. Clinicians will then decide on and prioritise management according to individual patient need.

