### 10.2 **Sample Size Considerations**

Our sample-size has been calculated to achieve a minimum 80% power ( $\alpha=0.05$ ) for our primary outcomes.

- Emergency presentations (measured from linked data that will be close to complete): Previous studies have reported reductions of 17-30% ([9] and personal communication). Assuming a similar baseline rate (1.09/person-year), we require 242 participants per group to detect a 20% reduction with 18 months follow-up.

- HR-QOL: To detect minimally-important differences (where there is no defined minimally-important difference we have used 0.5 standard deviations as recommended [32] we require 70-150 patients per group depending on the outcome. A sample of 200 per group will give >90% power for the primary outcomes in the full population and ~80% power for analyses stratified by e-PROM tool.

Allowing for up to 30% drop-outs (death or withdrawal), we will recruit a minimum of 572 participants (286 per group). We estimate that more than 2000 eligible patients will attend the study hospitals during a 12-month period (data from the Queensland Oncology Analysis System) thus this target is feasible.

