### 10.3.1 *Primary Outcomes*

**Fewer emergency presentations/unplanned hospital admissions:** we will use Poisson regression to calculate and compare the rate of unplanned hospital presentations (per 10,000 patient days) during follow-up in each group.

**Better physical and functional wellbeing:** we will calculate FACT-G physical and functional wellbeing scores at each time point. If there are missing items, subscale scores will be prorated as per the FACT-G scoring manual. We will compare mean scores in the two groups at 6 months using t-tests followed by general linear models to incorporate baseline covariates, including site, e-PROM tool, type of cancer, type of treatment (e.g. radio or chemotherapy). A difference of 0.5 standard deviations on each scale is considered clinically meaningful.

Differences at other time-points will also be assessed and we will explore changes over time and differences between treatment arms using a multilevel repeated measures model. The model for each post-randomisation point will be adjusted for baseline score and stratification factors.

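### Section 10.3.1 gives differently adjusted analyses of the primary 6-month wellbeing outcome, the first of them an unadjusted t-test, and does not say which one decides

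*Protocol*

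**What the plan says.** Section 10.3.1 describes three analyses that bear on 6-month physical and functional wellbeing.

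- **t-test, then linear model.** "We will compare mean scores in the two groups at 6 months using t-tests followed by general linear models to incorporate baseline covariates". The covariates named after this are site, e-PROM tool, cancer type and treatment type, the last illustrated by radiotherapy or chemotherapy. The list is introduced as examples, so it is open-ended.
- **Repeated-measures model.** The next paragraph turns to other time-points and change over time, using a multilevel model. It ends: "The model for each post-randomisation point will be adjusted for baseline score and stratification factors".

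Section 4.3.1 says randomisation is "stratified by sex, hospital, treatment intent (curative/palliative) and computer literacy". Of these four factors, only hospital (as site) is clearly in the linear model's list. Section 5.1 assigns one tool to each hospital: *My Health My Way* at PAH and TVH, *AboutMe* at RBWH and GCH.

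The baseline score is available. Section 4.3.1 triggers allocation when the baseline questionnaire is completed, Section 4.1.2 excludes consenting patients who do not complete it, and Appendix A lists FACT-G at T0.

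Section 10.3.2 follows the same pattern for FACT-G total, HADS and MSAS: t-tests at each time-point, with 6 months as the main one, then mixed models adjusted for baseline score and strata.

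**The concern.** A primary outcome needs one deciding analysis. Here a reader can find a t-test, a linear model with one covariate set and a repeated-measures model with another, and no stated order among them. If they disagree near the significance threshold, the protocol does not settle which result counts.

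The first-named analysis is also the least efficient. It uses neither the baseline score, which is usually the strongest predictor of a later score on the same scale, nor the stratification. When randomisation is balanced within strata that predict outcome, the true variance of the arm difference is smaller than the t-test assumes, so its standard error is too large.

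The listed linear model has a separate specification fault: site and e-PROM tool cannot both be estimated as fixed effects, because tool is determined by site.

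**Working it through.** **Inputs.** From Section 10.2: alpha 0.05 (taken as two-sided, which is not stated), minimum power 80%, 200 per group, and up to 30% drop-out giving 286 per group. From Section 10.3.1: a 0.5 SD difference is clinically meaningful. From Section 4.3.1: 1:1 allocation. No SD in scale points is given, so SD = 1. The baseline to 6-month correlation and the share of outcome variance explained by the strata are not in the protocol; both are assumptions, shown as ranges.

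**1. The plan's own figures.**
- Drop-out: 200/(1 − 0.30) = 285.7, so 286 per group, as stated.
- Power at 0.5 SD, unadjusted, 200 per group: Φ(0.5/√(2/200) − 1.96) = Φ(5.00 − 1.96) = 99.9%, consistent with the stated figure of above 90%.
- Size needed for 0.5 SD at 80% power: 2(1.96 + 0.8416)²/0.5² = 62.8, so 63 per group. The protocol says "we require 70-150 patients per group depending on the outcome"; 70 and 150 correspond to differences of 0.474 and 0.323 SD.

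These figures fit an unadjusted two-sample comparison.

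**2. Effect of adjusting for the baseline score.** The residual variance factor is 1 − r², the unadjusted equivalent of 200 per arm is 200/(1 − r²), and the 95% half-width is 1.96·√((2/200)(1 − r²)).

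| Assumed r | Variance cut | 200 per arm is worth | 95% half-width (SD) | Difference detectable at 80% power (SD) |
|---|---|---|---|---|
| none (t-test) | – | 200 | 0.196 | 0.280 |
| 0.4 | 16% | 238 | 0.180 | 0.257 |
| 0.5 | 25% | 267 | 0.170 | 0.243 |
| 0.6 | 36% | 312.5 | 0.157 | 0.224 |

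**3. Size of the t-test after stratified randomisation.** If the arms are balanced within strata and the strata explain a share R² of outcome variance, the large-sample two-sided size is 2(1 − Φ(1.96/√(1 − R²))). For assumed R² of 5%, 10% and 20% this is about 0.044, 0.039 and 0.028 instead of 0.05.

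**4. Site and tool together.** With four hospitals and one tool at each, an intercept, three site indicators and a tool indicator make 5 columns of rank 4. Adding arm gives 6 columns of rank 5. If tool is coded by site, the redundant column drops out and the arm estimate is unchanged. If tool were coded by actual use, with controls as non-users, it would be collinear with arm. The protocol does not say which coding is meant.

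**The case against.** **The linear model does not necessarily leave these covariates out.** A reader might infer that the primary analysis omits baseline score and most strata, and that the better model is reserved for secondary use. The text does not support that. The covariate list is open-ended. The adjustment sentence stands in the primary-outcome section and refers to each post-randomisation point, which read literally includes 6 months. Treatment type is also used loosely: Section 10.3.3 applies the phrase to curative versus palliative. This objection stands against any claim of omission. It does not remove the mismatch: if the sentence covers 6 months, there are competing analyses with different covariates; if it does not, the named list ignores the baseline score and at least two strata.

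**A separate analysis plan is promised.** Section 10.3 says one will be finalised before any analysis, and it may settle the matter. Absent detail would be no finding. But the protocol itself puts the t-test first and names specific covariates, so the fault is in what is written.

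**The harm is modest.** A t-test in a randomised trial is unbiased and here at worst conservative. Adjusted models do follow it. The precision gains rest on correlations that the protocol does not give. All of this stands.

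**Loss before 6 months.** A reader might infer that 30% of patients would be missing from the t-test. The 30% in Section 10.2 is a planning ceiling for death or withdrawal, with no 6-month time attached. Section 6.3 adds reminders and telephone completion, and 200 per group already allows for that loss. No 6-month figure is given.

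**Conclusion.** The point holds as an inconsistency in how the primary 6-month wellbeing analysis is specified. The section offers differently adjusted analyses without naming the deciding one, starts with the unadjusted one, and lists covariates that do not match its own adjustment sentence or the randomisation factors. The tool term is redundant beside site.

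The cost is an unclear primary inference, a conservative t-test (true size about 0.028 to 0.044 if the strata explain 20% to 5% of variance) and an interval wider than necessary: 0.196 SD against 0.157 to 0.180 SD for assumed correlations of 0.6 to 0.4.

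It would be tempting to call the comparison biased or under-powered. Neither is shown: power at 0.5 SD with 200 per group is already about 99.9% unadjusted. Precision matters more in the analyses by tool, for which Section 10.2 claims only about 80% power.

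**What to change.** In Section 10.3.1, before unblinding:

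- Name as the single primary analysis the 6-month difference between arms, adjusted for the baseline subscale score and the four stratification factors (hospital, sex, treatment intent, computer literacy). The repeated-measures model already described there can supply it.
- Keep the t-test as descriptive.
- Delete e-PROM tool as a main effect beside site. The planned subgroup analyses by tool can stay.

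In Section 10.3.2, use the same adjusted 6-month comparison for FACT-G total, HADS and MSAS.

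If the repeated-measures model is chosen, say how 6-month scores are interpreted for patients who have died, since such a model implicitly carries scores past death. A sensitivity analysis ranking deaths before 6 months as worst is optional and not part of this correction.

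The cost is wording in the protocol and the analysis plan. Every variable needed is already collected, and the sample size does not change.

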### 10.3.2 *Secondary Outcomes*

**Higher rates of treatment completion:** we will calculate the fraction of planned primary treatment that participants actually received. We will compare the mean (or median, as appropriate) fraction received and the proportion of participants who received >85% of their planned treatment between the groups using t-tests and chi-squared tests, respectively.

**Better overall HR-QoL, lower rates of distress and lower symptom burden:** we will calculate overall FACT-G (to measure HR-QoL), HADS anxiety and depression (to measure distress) and MSAS (to measure symptom burden) scores at each time point. If there are missing items, subscale scores will be prorated as per the relevant scoring manuals. We will use t-tests to compare the intervention and control groups with respect to absolute levels at each time-point (with 6 months being the primary time-point) and will use mixed effects repeated measures models to assess change over time from baseline. The models for post-randomisation point will be adjusted for baseline score and stratification factors. A difference of 0.5 standard deviations on each scale is considered clinically meaningful.

We will also assess differences in social and emotional wellbeing using these subscales of FACT-G.

**Fewer out-patient visits:** we will use Poisson regression to calculate and compare the rate of unplanned hospital presentations (per 10,000 patient days) during follow-up in each group.

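### Treatment completion is compared only by unstratified t-tests and chi-squared tests although randomisation is stratified; the tests stay valid but lose power to the extent that the strata predict completion

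*Protocol*

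**What the plan says.** Section 10.3.2 of the protocol defines treatment completion as the share of each participant's planned primary treatment that was actually received. It is summarised in two ways: the fraction itself, as a mean or, where suitable, a median, and "the proportion of participants who received >85% of their planned treatment". Both are compared "between the groups using t-tests and chi-squared tests, respectively". No adjusted or stratified analysis is named for this outcome.

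On allocation, section 4.3.1 has individual patients assigned 1:1 in blocks of varying size, and this allocation is "stratified by sex, hospital, treatment intent (curative/palliative) and computer literacy".

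For overall quality of life, distress and symptom burden, the same section 10.3.2 plans t-tests at each time point and also repeated-measures models: "The models for post-randomisation point will be adjusted for baseline score and stratification factors". In section 10.3.1 the t-test for the FACT-G primary outcome is followed by linear models with baseline covariates.

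Section 10.2 sets its power target for the primary outcomes. None is given for treatment completion.

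**The concern.** Stratified randomisation removes most of the chance imbalance between arms on the stratification factors. The estimated difference therefore varies less from trial to trial than it would under simple randomisation. An unstratified t-test or chi-squared test does not know this: it still counts the between-stratum variation as noise. Its standard error is too large, so it rejects less often than it should under the null and misses some real effects. A larger sample does not cure this, because the ratio of the assumed to the true variance does not depend on the sample size.

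At stake is some power on the first-listed secondary outcome, and a comparison that does not match the way patients were allocated. There is also a mismatch in the same sentence. It allows medians to be compared, but the only test it attaches to the fraction is a t-test, which compares means.

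**Working it through.** **Inputs from the protocol.** Recruitment is 286 per arm. Section 10.2 gives 200 per group and a 30% allowance for drop-out, and 200 / (1 − 0.30) = 285.7, rounded up to 286, so that figure reproduces. Alpha is 0.05; two-sided is assumed, as sidedness is not stated. The strata are sex (2) × hospital (4) × intent (2) × computer literacy (2) = 32 cells, so 572 / 32 is about 18 patients per cell. There is no stated power figure for treatment completion to reproduce.

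**Assumptions.** Half the patients are curative and half palliative (143 of each per arm), with exact balance within intent. Control completion rates by intent are assumed, because the protocol gives none. The odds ratio is 1.7 and common to both groups.

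**Step 1: how conservative the chi-squared test is.** With control rates pC (curative) and pP (palliative) and mean p = (pC + pP)/2, the share of outcome variance explained by intent is

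R² = ((pC − pP)/2)² / (p(1 − p)).

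Under balance, the unstratified statistic has true variance 1 − R² instead of 1, so its actual size is about 2[1 − Φ(1.96/√(1 − R²))].

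- 80%/70%: 0.0025 / 0.1875 = 0.013, size 4.8%
- 85%/65%: 0.0100 / 0.1875 = 0.053, size 4.4%
- 85%/50%: 0.0306 / 0.2194 = 0.140, size 3.5%
- 90%/40%: 0.0625 / 0.2275 = 0.275, size 2.1%

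**Step 2: simulation, chi-squared against Mantel-Haenszel stratified by intent, 286 per arm.**

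| Control completion, curative/palliative | Size, chi-squared vs MH | Power, chi-squared vs MH |
|---|---|---|
| 80%/70% | 4.9% vs 5.1% | 71% vs 72% |
| 85%/65% | 4.5% vs 5.0% | 69% vs 71% |
| 85%/50% | 3.5% vs 5.0% | 71% vs 75% |
| 90%/40% | 2.0% vs 4.9% | 61% vs 72% |

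The simulated sizes agree with Step 1 to within about 0.1 percentage point. If completion is the same in both intent groups (75%/75%), the two tests coincide.

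**Step 3: does the result survive 32 small cells?** Allocating 572 patients over 32 equally likely cells in permuted blocks of 4 or 6 (block sizes assumed), with the same odds ratio, gives size 4.4% vs 5.0% and power 69% vs 71% at 85%/65%, and size 3.5% vs 4.9% and power 71% vs 75% at 85%/50%. Incomplete blocks barely change the result.

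**Step 4: the t-test on the fraction.** Take a true difference of 1.960 + 0.842 = 2.802 nominal standard errors, that is, 80% nominal power. The unadjusted test then has power Φ(0.842/√(1 − R²)) and the adjusted model Φ(2.802/√(1 − R²) − 1.960).

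- R² = 0.02: size of the unadjusted test 4.8%; power 80.2% vs 80.8%
- R² = 0.10: size 3.9%; power 81.3% vs 84.0%
- R² = 0.30: size 1.9%; power 84.3% vs 91.8%

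**The case against.** The other side has a good deal of force.

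- **The size rests on assumed rates.** A reader might infer that completion is driven by treatment intent. The protocol does not say so and gives no completion rates. The outcome is measured against each patient's own plan, which may narrow any gap between curative and palliative patients. For gaps of 20 points or less, the loss in the table is 2 points or less. This stands, and it is why the range has to start near zero.
- **Nothing is invalid.** A reader might infer that the error rate is wrong in a harmful way. It is not: type I error stays at or below 5%, and an unadjusted comparison in a randomised trial is unbiased. This stands.
- **No promised power is missed.** Section 10.2 says "Our sample-size has been calculated to achieve a minimum 80% power", and that is for the primary outcomes. A reader cannot infer a shortfall against a target for this outcome. This stands.
- **The contrast with other outcomes is partial.** Quality of life, distress and symptoms also get plain t-tests; only their repeated-measures models are adjusted. Out-patient visits and survival name no adjustment either. This stands, but those three outcomes do have an adjusted model beside the t-test, and treatment completion has none. The subgroup analyses in section 10.3.3 cover intent, site, sex and computer literacy, but repeating a test within subgroups is not a stratified overall test.
- **The formal analysis plan may settle it.** Section 10.3 promises one before any analysis, and detail left to it is no fault here. But the protocol does not leave this method open: it names the tests.

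**Conclusion.** The point holds as one of efficiency and consistency. The protocol fixes tests for treatment completion that ignore the factors on which patients were randomised. The tests are valid but conservative. The power given up, for an odds ratio of 1.7 and 286 per arm, runs from about 1 point (80%/70% completion by intent) to about 11 points (90%/40%), and is nil if the strata do not predict completion. These figures rest on assumed completion rates, an assumed even split by intent and stratification on intent alone. Hospital, sex and computer literacy would add to the gain only as far as they too predict completion.

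The mismatch between medians and a t-test needs correcting whatever the strata do, but it is a small matter of wording.

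**What to change.** Make these the main comparisons for treatment completion, in the protocol or the analysis plan, before any data are analysed:

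- **Fraction received:** a linear model with arm and the stratification factors. If the fraction is skewed and medians are reported, use a rank test, preferably stratified.
- **Proportion above 85%:** either a Mantel-Haenszel test by the main strata (for example intent and hospital, which makes 2 × 4 = 8 strata; all 32 cells would be sparse), or a regression with the stratification factors as main effects, reported as a standardised (marginal) risk difference.

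The plain t-test and chi-squared test can stay as supporting analyses.

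No new data are needed, because the factors are recorded at randomisation. The cost is slightly more analysis work. There is one trap: logistic regression reported without standardisation gives a conditional odds ratio, which is a different quantity from the difference in proportions that the present text compares.

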### 10.3.3 *Exploratory Outcomes*

**Survival:** we will calculate and the mortality rate (per person-year) in each group and use Cox proportional hazards regression to compare mortality in the two study groups.

**A better patient care experience:** the AHPEQS asks patients to rate 9 aspects of care on a 5-point scale from never (worst) to always (best) and their overall care from very poor to very good. We will use chi-squared tests to compare the proportions of participants in each group that answer mostly or always to each individual item (or good/very good to overall care) and t-tests to compare the mean number of items rated as mostly/always. We will also

compare the proportions of participants who report experiencing physical and/or emotional distress and, among those who report distress, the proportions who reported that healthcare staff discussed this with them.

**Partner/Carer distress and unmet supportive-care needs:** HADs data from carers will be analysed as for participants (above). Analyses of supportive-care needs will compare the frequency of individual needs and specific domains (information needs, healthcare needs, psychological and emotional needs, social and work needs). Parametric and non-parametric tests, as appropriate, will be used to compare the intervention and control groups.

**Sub-group analyses:** We will repeat the primary and secondary analyses above for sub-groups of participants defined by (i) study site, (ii) e-PROM tool (*My Health My Way* vs. *AboutMe*), (iii) cancer type (high vs. low mortality), (iv) type of treatment (curative/palliative), (v) sex, and (vi) computer literacy. This is to examine effect modification and identify scenarios where e-PROM tools are potentially most effective and those where their effectiveness could be improved. We recognise that statistical power will be more limited for some of these stratified comparisons.

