##### **3.4.1 *Extended passive follow-up***

After the end of the active follow-up period, we will continue to monitor ongoing use of the e-PROM tools for an additional 12 months and will follow participants passively (through medical records and routine data linkage) for up to an additional 5 years. There will be no further contact with participants during this period. We will also conduct a brief survey with a sample of clinicians at each of the study sites at 6 and 12 months after study. This will ask whether the clinicians are still using the tools, how many and which patients they use them with (e.g. only former trial participants or also new patients), how often they use them and how they use the results.

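### The survival Cox model in 10.3.3 names no strata; fitted as written across curative and palliative patients, it would pull the hazard ratio toward 1 and give a conservative test

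*Protocol*

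**What the plan says.** The survival analysis takes one sentence in section 10.3.3: mortality rates per person-year in each group, then "use Cox proportional hazards regression to compare mortality in the two study groups". No strata or covariates are named.

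Section 4.3.1 says that randomisation is "stratified by sex, hospital, treatment intent (curative/palliative) and computer literacy". For the FACT-G repeated-measures model, section 10.3.1 says "The model for each post-randomisation point will be adjusted for baseline score and stratification factors". Section 10.3.2 says the same of the other questionnaire scores: "The models for post-randomisation point will be adjusted for baseline score and stratification factors".

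The sub-group analyses in 10.3.3 include curative versus palliative treatment, but they repeat only the primary and secondary analyses. Survival is exploratory, so they do not cover it.

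On timing, section 2.3.3 says survival will be assessed passively after the main trial, and section 3.4.1 allows passive follow-up "for up to an additional 5 years". Section 6.4 does not routinely offer controls the tool at the end, so that the groups can be followed long term for survival.

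**The concern.** Treatment intent is probably the strongest predictor of death among the randomisation factors. Leaving it out of a Cox model has two consequences.

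- **The hazard ratio shrinks.** The arms are balanced on intent at entry. If the intervention reduces mortality equally in both intent groups, the intervention arm keeps more of its high-risk palliative patients as time passes. Its average hazard then rises relative to the control arm. The pooled hazard ratio drifts toward 1 and hazards stop being proportional, even though the effect within each group is constant.
- **The test becomes conservative.** Stratified allocation removes chance imbalance in intent between the arms. A pooled model does not credit that balance in its standard error.

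Better survival is one of the stated hypotheses (2.4 and 10.1). Both effects grow with follow-up, and long follow-up is what the protocol plans for this outcome.

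**Working it through.** **Inputs from the protocol.** 1:1 allocation at patient level with intent as a stratum (4.3.1); 572 patients and alpha 0.05 (10.2); active follow-up of 18 months, or 24 if funded (3.4); up to 5 more years passively (3.4.1), so at most 24 + 60 = 84 months.

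**Reproducing the stated sample size.** 200 / (1 − 0.30) = 285.7, rounded up to 286 per group and 572 in total. This agrees with 10.2. The protocol gives no event count, hazard ratio or power for survival, so there is nothing further to reproduce.

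**Assumptions, not in the protocol.** Within-group hazard ratio 0.75 in both intent groups, constant over time; 50% palliative; palliative median survival 12 or 18 months; curative median a multiple of that; exponential survival; censoring only at the end of follow-up; two-sided test; 1:1 allocation within intent groups.

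**Method.** Simulate 572 patients, then fit a one-covariate Cox model pooled and stratified by intent (2,500 runs per scenario, so the simulation error on a power near 50% is about √(0.25/2500) = 1 point). Results with a palliative median of 12 months:

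| Curative : palliative median | Follow-up (months) | Deaths | Pooled HR | Power pooled | Power stratified | Loss (points) |
|---|---|---|---|---|---|---|
| 2 | 18 | 274 | 0.756 | 63.0% | 66.3% | 3.3 |
| 2 | 84 | 531 | 0.768 | 87.7% | 91.2% | 3.5 |
| 3 | 18 | 245 | 0.765 | 54.7% | 60.4% | 5.7 |
| 3 | 84 | 496 | 0.789 | 78.1% | 89.0% | 10.9 |
| 5 | 18 | 217 | 0.775 | 46.2% | 56.5% | 10.3 |
| 5 | 84 | 444 | 0.815 | 58.0% | 84.8% | 26.8 |
| 10 | 18 | 195 | 0.788 | 35.1% | 51.2% | 16.1 |
| 10 | 84 | 380 | 0.853 | 27.2% | 80.2% | 53.0 |

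The stratified model returned a hazard ratio of about 0.75 throughout. At a 10-fold gap, pooled power falls from 35.1% to 27.2% between 18 and 84 months, although deaths nearly double.

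Over all runs with 50% palliative (adding the 18-month palliative median for gaps up to 5-fold, and follow-up of 24 months), the loss is about 1 to 4 points at 2-fold, 4 to 12 at 3-fold, 6 to 27 at 5-fold and 16 to 53 at 10-fold. The log hazard ratio shrinks by 2 to 9%, 5 to 17%, 8 to 29% and 17 to 45% respectively. With 30 to 70% palliative and gaps of about 7- to 15-fold, the loss is about 4 to 65 points.

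**Check of the stratified power.** Schoenfeld: power = Φ(|ln HR| × √(deaths/4) − 1.96). For 245 deaths: 0.2877 × √61.25 − 1.96 = 0.29, which gives 61%, against 60.4% simulated.

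**Under no effect.** With 50% palliative, a 10-fold gap and 4,000 runs, the pooled test rejects 1.0% of the time at 24 months and 0.3% at 84 months. The stratified test rejects 5.0% at both.

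**The case against.** The strongest case against is that 10.3.3 is silent and states nothing false. A reader might infer that the protocol prescribes an unstratified model. It does not: it names Cox regression and the two groups, and section 10.3 defers detail to an analysis plan that is not shown and could add strata. The contrast with the questionnaire models is also incomplete, because the Poisson models, t-tests and chi-squared tests name no stratification factors either.

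Survival is exploratory, section 2.3.3 accepts lower power for some exploratory outcomes, and the claim "Our sample-size has been calculated to achieve a minimum 80% power" concerns the primary outcomes only.

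The size of the loss is assumed as well. A common hazard ratio held constant to 84 months is generous to the stratified model. Tool use at Townsville and Gold Coast is currently supported only during the trial (4.4.4), and controls who ask for the tool can have it (6.4). If the effect differs by intent, there is no single common hazard ratio to recover. The pooled ratio is also a legitimate marginal quantity and not simply a wrong estimate of the conditional one.

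All of this stands and limits the point. It does not remove it: the protocol does specify adjustment for some models, nothing in it covers survival, and the model as written is the weaker choice in every scenario run.

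**Conclusion.** The point holds as a low-to-moderate improvement to an exploratory analysis. Fitted as written, with a similar effect in both intent groups, the Cox model gives a hazard ratio nearer 1 and a conservative test. The cost is minor if the prognostic gap is about 2-fold. It can be large at 5-fold or more over the long passive follow-up. The palliative share, median survival and hazard ratio behind these figures are assumptions.

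Three stronger readings are not supported:

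- That much of the power is lost whatever the case mix. This needs a large prognostic gap, which the protocol does not document.
- That the pooled analysis risks a false positive. Under no effect it rejects too rarely.
- That stratifying makes the survival comparison adequately powered. The medians of 31 and 26 months quoted in 2.1 imply a hazard ratio of about 26/31 = 0.84 if survival is exponential. By Schoenfeld, a ratio of 0.83 needs 905 deaths for 80% power, more than the 572 patients. Simulated stratified power at 0.83 was 19 to 51%.

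No figure stated in the protocol is wrong.

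**What to change.** In 10.3.3, state that the reported hazard ratio for survival comes from a Cox model stratified by treatment intent and adjusted for the other randomisation factors (hospital, sex, computer literacy), with a log-rank test stratified by intent. Carry the same wording into the statistical analysis plan.

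Stratifying by intent alone and adjusting for the rest is preferable to stratifying by all four factors. The full cross-classification has 2 × 4 × 2 × 2 = 32 cells, an average of 572/32 ≈ 18 patients each, and many cells would contribute few deaths.

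The cost is one sentence. All four factors are recorded before randomisation, so no new data are needed and the sample size does not change.
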